1.1 Study Design

A phase II trial of BVD-523 in patients with metastatic uveal melanoma. Patients will receive twice daily oral dosing of BVD-523 at the recommended phase II dose in 28-day treatment cycles until disease progression, unacceptable toxicity or other withdrawal criteria is met. Total enrollment for this phase II trial will be 13 or 25 patients.

1.2 Primary Objectives

1. To evaluate the overall response rate in uveal melanoma to ERK inhibitor therapy with BVD-523.

1.3 Secondary Objectives

1. To characterize the safety profile of ERK inhibitor therapy with BVD-523 when administered to adult patients with unresectable or metastatic uveal melanoma
2. To evaluate overall survival of patients with uveal melanoma treated with ERK inhibitor therapy with BVD-523.
3. To evaluate the pharmacodynamics of ERK inhibition on BVD-523 with a comparison of pre- and on-treatment biopsies.
4. To better understand the genetic variability of uveal melanoma through whole exome sequencing.

BACKGROUND

2.1 Study Disease(s)

In 2014 approximately 76,100 new cases of malignant melanoma were diagnosed in the United States.¹ While the majority of these arise from melanocytes of cutaneous origin, ocular melanomas comprise approximately 5% of all melanomas.² Uveal melanoma is a rare malignancy that arises from the iris, ciliary body or choroid of the eye. Ocular melanoma tumors may also arise in association with nevus of Ota.³

Management of uveal melanomas differs from that of cutaneous melanoma, as only inconsistent responses are seen to the therapies used most commonly for cutaneous melanoma, including ipilimumab, the anti-PD1 antibodies nivolumab and pembrolizumab, and chemotherapy. Despite the ability to achieve local control in the majority of patients, a quarter of patients will go on to die of metastatic disease.⁴ The most common sight of initial metastasis is the liver due to hematogenous spread with an average survival of approximately one year after metastatic disease is diagnosed.⁵

Since uveal melanomas respond poorly to chemotherapy and immunotherapy no effective treatment options exist for this group of patients who develop metastatic disease. Most patients

with metastatic disease are considered for Phase I clinical trials as first line therapy. Unlike cutaneous melanoma, BRAF mutations are rarely (if ever) observed in uveal melanoma. However, greater than 80% of uveal melanomas have activating mutations in GNAQ or GNA11, genes that encode for G protein alpha subunits.⁶⁻⁸ GNAQ and GNA11 mutations lead to downstream signaling through the MAPK pathway.

2.2 IND Agent

BVD-523 is a small molecule that potently inhibits both ERK1 and ERK2 protein kinases in the sub-nanomolar range, while not significantly inhibiting any of an array of kinases even at 1000-fold greater concentrations. BVD-523 potently inhibits growth and survival in cultured cancer cell lines; melanoma, colorectal and pancreatic lines harboring BRAF or RAS mutations are among those most susceptible to the drug. In animals bearing ectopic tumor xenografts, orally administered BVD-523 is effective as a single agent, again preferentially in cancers where activating mutations in the MAPK pathway cause abundant ERK kinase activation.

A phase I study of BVD-523 in patients with advanced malignancies (BVD-523-01) is currently ongoing and has demonstrated activity in patients with BRAF/MEK-inhibitor refractory, BRAF-mutant melanoma as well as in patients with NRAS-mutant melanoma. The dose-escalation phase of this study has been completed and the study has moved into a cohort-expansion part 2. This dose-escalation phase included dose levels ranging from 10 to 900 mg b.i.d. Single-patient cohorts were completed for dose levels of 10 mg, 20 mg, 40 mg, 75 mg, and 150 mg b.i.d. Subsequent cohorts included 4 patients (300 mg b.i.d.), 7 patients (600 mg b.i.d.), 4 patients (750 mg b.i.d.), and 7 patients (900 mg b.i.d.). Intra-patient dose escalation was permitted once the next higher dose had been declared tolerable; this occurred in 5 patients, including 4 patients who dose-escalated more than one time. The total duration of exposure has ranged from 23 to 804 days; the median duration of exposure to date is 93.0 days. The patient population in Part 1 included 14 males (52%) and 13 females (48%), ranging in age from 32 to 84 years old (mean age 59.7 years), diagnosed with a range of advanced solid tumors. In Part 1, the MTD and RP2D were determined to be 600 mg b.i.d., and this is the dose that is being tested in the cohort-expansion phase (Part 2) of the study. Two patients remained active on Part 1 study as of the cut-off date of 16th January 2016 and 48 patients have been enrolled and treated in Part 2 of Study BVD-523-01 which expands the 600 mg b. i. d. cohort to 7 groups of cancer patients with various BRAF, NRAS, MEK, and ERK mutations.

A second phase I study of BVD-523 in participants with acute myelogenous leukemia (AML) or myelodysplastic syndrome (MDS) also reached a MTD and RP2D of 600 mg b. i. d. The dose-escalation phase (Part 1) of this second study, BVD-523-02 has been completed, with 18 patients having been enrolled in this part of the study. This dose-escalation phase included dose levels ranging from 300 to 750 mg b.i.d. Cohorts evaluated included 5 patients (300 mg b.i.d.), 6 patients (600 mg b.i.d.), and 7 patients (750 mg b.i.d.). As of 16th January 2016, 3 patients (2 female, 1 male; age range 48 to 77 years old) have been enrolled into the cohort-expansion phase (Part 2) of Study BVD-523-02. As in Part 1, patients in Part 2 are required to have AML or MDS and are receiving BVD-523 at the dose of 600mg b. i. d. determined in Part 1.

BVD-523 will be administered at the RP2D of 600mg twice daily in 28 day cycles. The HCl salt of BVD-523 was selected for manufacture of drug product in capsule form.

More information is available in the Investigator's Brochure for BVD-523.

2.3 Rationale

The mitogen-activated protein kinase, or MAPK, pathway is a cell growth control pathway frequently aberrantly activated in malignancy. Surface receptors signal through RAS family GTPases to RAF family protein kinases, MEK and subsequently ERK family kinases. ERK kinases activate an array of effectors which lead to cell division and survival.⁹ Many different components of the MAPK pathway can be mutated in cancer leading to activation of the pathway including members of the RAS family GTPase (KRAS, NRAS, and HRAS) and BRAF which is seen in over 50% of patients with advanced melanoma.^{10, 11} Targeting the MAPK pathway has demonstrated efficacy in patients with mutations leading to increased MAPK signaling. Specifically there has been efficacy targeting BRAF in melanoma patients with a BRAF mutation¹² and even more efficacy when BRAF and MEK are targeted simultaneously.^{13, 14}

Uveal melanomas have a high rate of activating mutations in GNAQ or GNA11 leading to downstream signaling through the MAPK pathway⁶⁻⁸. This has led to therapeutic targeting of the MAPK pathway with MEK inhibition in patients with uveal melanoma. In a randomized phase II trial, 99 patients were randomized to receive the MEK inhibitor selumetinib or chemotherapy (investigator's choice of dacarbazine or temozolomide). Treatment with selumetinib was associated with a PFS of 15.9 versus 7 weeks with chemotherapy, and objective response rates of 14% and 0%, respectively.¹⁵ Analysis of patients treated on this study supported a MAPK dependence which was reflected in MEK-Dependent gene expression changes in response to therapy.¹⁶

The ERK family kinases are MAPK signaling components downstream of MEK that have yet to be targeted in clinical practice, and ERK activation in Uveal melanoma has been observed in relation to GNAQ and GNA11 mutations.^{6, 7} In addition ERK inhibition has been seen to overcome acquired resistance to MEK inhibitors in preclinical studies.¹⁷ BVD-523 is a small – molecule inhibitor of ERK kinase currently in Phase I testing that has demonstrated activity in patients with BRAF/MEK-inhibitor refractory, BRAF-mutant melanoma as well as in a patient with NRAS mutant melanoma. Given the role of the MAPK pathway on development and growth of uveal melanoma and the initial activity in other MAPK dependent melanoma settings, there is a high probability that BVD-523 would have efficacy in this disease.

2.4 Correlative Studies Background

In order to evaluate the pharmacodynamics of ERK inhibition with BVD-523 we will obtain tissue samples from patients prior to enrollment and after approximately 15 days on treatment. These biopsies will be assessed by western blotting, to look at levels of ERK targets including DUSP, cyclin D, and others, and RNA seq to evaluate gene expression analysis. The goal of this correlative work is to determine if BVD-523 is appropriately inhibiting downstream signaling through ERK. In addition this testing will allow us to look at mechanisms of resistance to ERK

inhibition and predictors of response. In addition tumor will be assessed for the presence or absence of GNAQ and GNA11 mutations allowing for correlation with outcome.

Our understanding of the genetics of uveal melanoma is limited. A better understanding of the genetic diversity of uveal melanoma would be valuable to guide therapy and combinations of therapy in the future. We plan to perform whole exome sequencing in collaboration with the Broad Institute to gain a better understanding of the drivers of uveal melanoma

PARTICIPANT SELECTION

In this phase II study up to 25 patients with metastatic uveal melanoma will be enrolled to evaluate the efficacy of BVD-523. In the first stage 13 patients will be enrolled at which time an initial evaluation for efficacy will be performed. If sufficient efficacy is seen, we will enroll an additional 12 patients for a total of 25.

3.1 Eligibility Criteria

- 3.1.1 Participants must have histologically or cytologically confirmed stage IV uveal melanoma.
- 3.1.2 Participants must have measurable disease, defined as at least one lesion that can be accurately measured in at least one dimension (longest diameter to be recorded for non-nodal lesions and short axis for nodal lesions) as ≥ 20 mm with conventional techniques or as ≥ 10 mm with spiral CT scan, MRI, or calipers by clinical exam. See Section 11 for the evaluation of measurable disease.
- 3.1.3 Patients can have received any number of prior therapies for treatment of their uveal melanoma excluding prior treatment with an ERK inhibitor. Patients who have received prior MEK inhibition or other MAPK targeted agents will be allowed on study.
- 3.1.4 Age ≥ 18 years of age.
- 3.1.5 ECOG performance status ≤ 2 (Karnofsky $\geq 60\%$, see Appendix A)
- 3.1.6 Life expectancy of greater than 6 months
- 3.1.7 Participants must have normal organ and marrow function as defined below:
- leukocytes $\geq 3,000/\text{mcL}$
 - hemoglobin $\geq 9.0 \text{ g/dL}$
 - absolute neutrophil count $\geq 1,500/\text{mcL}$
 - platelets $\geq 100,000/\text{mcL}$
 - total bilirubin $\leq 1.5 \times$ institutional upper limit of normal
 - AST(SGOT)/ALT(SGPT) $\leq 2.5 \times$ institutional upper limit of normal, unless there is known liver involvement in which case $\leq 5.0 \times$ institutional upper limit of normal
 - creatinine within normal institutional limits

OR

- creatinine clearance ≥ 60 mL/min/1.73 m² for participants with creatinine levels above institutional normal.
- 3.1.8 Participants must have adequate cardiac function, e.g. left ventricular ejection fraction (LVEF) of >50% as assessed by multi-gated acquisition (MUGA) or ultrasound/echocardiography (ECHO); corrected QT interval (QTc) <470ms.
- 3.1.9 Presence of metastatic disease that would be amenable to the required biopsies. Ideally pre and post biopsies should be from the same lesion and otherwise from lesions in the same organ. If not possible, then biopsy of the lesions in different organs will be permitted. Archival tissue from a biopsy taken within 6 months prior to the first study treatment may be used in place of a pre-treatment biopsy at the discretion of the principal investigator.
- 3.1.10 The effects of BVD-523 on the developing human fetus are unknown. For this reason and because ERK inhibitors could potentially be teratogenic, women of child-bearing potential and men must agree to use adequate contraception (hormonal or barrier method of birth control; abstinence) prior to study entry, for the duration of study participation, and 4 months after completion of BVD-523 administration. Should a woman become pregnant or suspect she is pregnant while she or her partner is participating in this study, she should inform her treating physician immediately. Men treated or enrolled on this protocol must also agree to use adequate contraception prior to the study, for the duration of study participation, and 4 months after completion of BVD-523 administration.
- 3.1.11 Ability to understand and the willingness to sign a written informed consent document.

3.2 Exclusion Criteria

- 3.2.1 Participants who have had chemotherapy or radiotherapy within 4 weeks (6 weeks for nitrosoureas or mitomycin C), small molecule targeted therapy (i.e. – kinase inhibitors) within 3 weeks or the last dose of antibody therapy within 4 weeks prior to entering the study or those who have not recovered from adverse events due to agents administered more than 4 weeks earlier.
- 3.2.2 Participants who are receiving any other investigational agents.
- 3.2.3 Major surgery within 4 weeks of the first dose of BVD-523. Tumor embolization procedure or ablation procedure within 2 weeks of first dose of BVD-523.
- 3.2.4 Participants with known brain metastases or evidence of leptomeningeal involvement are eligible only if these lesions are treated and both clinically and radiographically stable for at least four weeks. Patients are eligible if they are being treated with a stable dosage of steroids/anticonvulsants, requiring no dose increase for 4 weeks.

- 3.2.5 History of allergic reactions attributed to compounds of similar chemical or biologic composition to BVD-523.
- 3.2.6 Participants receiving any medications or substances that are known to be strong inhibitors of CYP1A2, CYP2D6, and CYP3A4 or strong inducers of CYP3A4 are ineligible. Because the lists of these agents are constantly changing, it is important to regularly consult a frequently-updated list such as <http://medicine.iupui.edu/clinpharm/ddis/table.aspx>; medical reference texts such as the Physicians' Desk Reference may also provide this information. As part of the enrollment/informed consent procedures, the patient will be counseled on the risk of interactions with other agents, and what to do if new medications need to be prescribed or if the patient is considering a new over-the-counter medicine or herbal product.
- 3.2.7 Uncontrolled intercurrent illness including, but not limited to, ongoing or active infection, symptomatic congestive heart failure, unstable angina pectoris, cardiac arrhythmia, or psychiatric illness/social situations that would limit compliance with study requirements.
- 3.2.8 Pregnant women are excluded from this study because BVD-523 is an ERK with the potential for teratogenic or abortifacient effects. Because there is an unknown but potential risk for adverse events in nursing infants secondary to treatment of the mother with BVD-523 breastfeeding should be discontinued if the mother is treated with BVD-523.
- 3.2.9 Gastrointestinal (GI) condition which could impair absorption of study medication or inability to ingest study medication.
- 3.2.10 A history of current evidence/risk of retinal vein occlusion (RVO) or central serous retinopathy (CSR)
- 3.2.11 Concomitant malignancies or previous malignancies with less than 2 years of disease-free interval at the time of enrollment (except non-melanoma skin cancer, cervical cancer in situ, prostate cancer with undetectable PSA). Other concurrent malignancies must be discussed with the medical monitor prior to enrollment.
- 3.2.12 Patients with melanoma of cutaneous, mucosal or acral-lentiginous origin or of unknown primary.

3.3 Inclusion of Women and Minorities

Both men and women of all races and ethnic groups are eligible for this trial.

REGISTRATION PROCEDURES

4.1 General Guidelines for DF/HCC Institutions

Institutions will register eligible participants in the DF/HCC Clinical Trial Management System

(CTMS) OnCore. Registrations must occur prior to the initiation of protocol therapy. Any participant not registered to the protocol before protocol therapy begins will be considered ineligible and registration will be denied.

An investigator will confirm eligibility criteria and a member of the study team will complete the protocol-specific eligibility checklist.

Following registration, participants may begin protocol therapy. Issues that would cause treatment delays should be discussed with the Overall Principal Investigator (PI). If a participant does not receive protocol therapy following registration, the participant's registration on the study must be canceled. Registration cancellations must be made in OnCore as soon as possible.

4.2 Registration Process for DF/HCC Institutions

DF/HCC Standard Operating Procedure for Human Subject Research Titled *Subject Protocol Registration* (SOP #: REGIST-101) must be followed

TREATMENT PLAN

5.1 Treatment Regimen

BVD-523 is to be taken twice daily orally for 28 consecutive days at 12 ±2 hour intervals. This will be dosed at the recommended phase 2 dose (RP2D) of 600mg twice daily. This study drug dose will be supplied to participants in four 150 mg capsules 28 consecutive days will be defined as a treatment cycle. Treatment will be administered on an outpatient basis. The study medication should be taken with 8 ounces of water (Juice, coffee, tea or soda is not allowed) at the same time each day on an empty stomach i.e., fasting (30-60 minutes before food or 2 hours after food). At this time, there are no identified foods that participants should avoid while taking study drug. All capsules, if more than one is taken at each dosing time, should be taken within 10 minutes. Patients will be instructed NOT to take a substitute capsule if vomiting occurs after self-dosing at home. In clinic doses are only required on days when PK samples are collected. Dosing initiates the clock for PK collections.

Reported adverse events and potential risks are described in Section 7. Appropriate dose modifications are described in Section 6. No investigational or commercial agents or therapies other than those described below may be administered with the intent to treat the participant's malignancy.

5.2 Pre-Treatment Criteria

5.2.1 Screening visit

All participants must sign an informed consent document prior to the initiation of any study related procedures. The informed consent document must be signed within 30 days of Cycle 1 Day 1. The remaining screening procedures (with the exception of the scans

and pre-treatment biopsy) are to be conducted within 21 days of Cycle 1 Day 1.

- Review of study eligibility criteria
- Physical Examination, including height and weight
- Medical History
- Record concomitant medications taken up to 14 days prior to Cycle 1 Day 1
- Vitals [temperature, heart rate (HR), blood pressure (BP) and respiratory rate (RR)]
- ECOG Performance Status evaluation
- Laboratory Assessments
 - Hematology: hemoglobin, hematocrit, red blood cell count, white blood cell count with differential and platelet count
 - Serum chemistry: sodium, potassium, chloride, bicarbonate, magnesium, calcium, phosphorus, blood urea nitrogen, creatinine, glucose (random), total bilirubin, LDH, total protein, ALP, ALT, AST, creatine phosphokinase, and albumin
 - Serum lipase and amylase
 - Serum pregnancy test for women of childbearing potential (WOCBP)
 - Prothrombin time (PT) and activated partial thromboplastin time (aPTT)
 - Urinalysis
- Echocardiogram (ECHO)
 - Unscheduled ECHOs can be completed as clinically indicated.
- 12-lead ECG. If an ECG shows QTc prolongation (>470 milliseconds), the ECG must be repeated twice to obtain values in triplicate.
- Ophthalmology examination: an ophthalmologist, or designated member of the clinical team, will check the participants vision and measure the pressure level in their eyes at baseline.
- Radiologic imaging studies to evaluate tumor status must include: Magnetic Resonance Imaging (MRI) of the brain and contrast Computed Tomography (CT) of the chest, abdomen, and pelvis. MRI of the chest, abdomen and/or pelvis may be used in place of a CT scan at baseline, but the same type of imaging modality must then be used throughout the course of the study (e.g. MRI of the pelvis performed at baseline, therefore, MRI of pelvis must be done at subsequent visits). Additional imaging may be obtained as clinically indicated. Baseline scans must be done ≤ 4 weeks prior to the start of study treatment.
- Tumor biopsy 1 – 28 days prior to receiving the first dose of study treatment. Archival tissue from a biopsy taken within 6 months prior to the first study treatment may be used in place of a pre-treatment biopsy at the discretion of the PI.

5.2.2 Cycle 1, Day 1

- Physical exam
- Vital signs (temperature, HR, BP and RR)
- Weight
- Performance status
- Record concomitant medications
- Laboratory Assessments*
 - Hematology
 - Serum chemistry
 - Serum lipase and amylase
 - Serum pregnancy test for WOCBP
- 12-lead ECG. If an ECG shows QTc prolongation (>470 milliseconds), the ECG must be repeated twice to obtain values in triplicate.
- BVD-523 dosing
- Dispensing of study medication for the remainder of the 28 day cycle with drug diary.
- Record AEs

***NOTE:** C1D1 laboratory assessments are not required to re-meet eligibility criteria. If there is a cause for concern related to eligibility or scheduled C1D1 laboratory assessments the investigator should use their discretion.

5.2.3 Cycle 1, Day 15

- Tumor biopsy between days 12-18 while on treatment.
- Collection of research blood sample for PK analysis prior to dosing.

5.2.4 Cycle 2, Day 1

- Physical exam
- Vitals (temperature, HR, BP and RR)
- Weight
- Performance status
- Record concomitant medications
- Laboratory Assessments
 - Hematology

- Serum chemistry
- Serum lipase and amylase
- PT and aPTT
- Urinalysis
- Serum pregnancy test for WOCBP
- 12-lead ECG. If an ECG shows QTc prolongation (>470 milliseconds), the ECG must be repeated twice to obtain values in triplicate.
- BVD-523 dosing
- Dispensing of medication for the remainder of the 28 day cycle with drug diary.
- Record AEs
- Eye examination

5.2.5 Cycle 2, Days 22 – 28

- Radiologic imaging studies: CT or MRI of chest, abdomen and pelvis followed by response evaluation to evaluate tumor status are required at each tumor assessment visit, even if sites of disease were not identified in this region at baseline. MRI scan of the brain and additional imaging may be obtained as clinically indicated.

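### The archival-tissue rule lets a biopsy taken on a prior MEK or other MAPK inhibitor serve as the baseline for the ERK-signalling comparison

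*Combined protocol and SAP*

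**What the plan says.** - **Who may enter.** Section 3.1.3: "Patients who have received prior MEK inhibition or other MAPK targeted agents will be allowed on study". Only a prior ERK inhibitor is barred.
- **Washout.** Section 3.2.1 excludes patients with small-molecule targeted therapy ("kinase inhibitors) within 3 weeks or the last dose of antibody therapy within 4 weeks prior to entering the study"). Entry is not defined. Section 3.2.3, by contrast, counts from dosing: "Major surgery within 4 weeks of the first dose of BVD-523".
- **Fresh baseline.** Section 5.2.1: "Tumor biopsy 1 – 28 days prior to receiving the first dose of study treatment". Section 9.0 gives 7 to 28 days.
- **Archival substitute.** Section 5.2.1: "Archival tissue from a biopsy taken within 6 months prior to the first study treatment may be used in place of a pre-treatment biopsy". The principal investigator decides whether to allow it. Sections 3.1.9 and 9.0 and note i of the 10.1 calendar say the same.
- **Purpose.** Section 2.4: "The goal of this correlative work is to determine if BVD-523 is appropriately inhibiting downstream signaling through ERK". Secondary objective 3 in 1.3 is the comparison of pre- and on-treatment biopsies.
- **Analysis.** Section 13.6 relates both the pre-treatment level and the percent change to outcome. It plans on 23 pairs, 6 responders and 17 non-responders, and has no rule for a baseline taken on an inhibitor.

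**The concern.** The comparison can show what BVD-523 does to ERK signalling only if the first sample was taken without another drug acting on the same pathway. Section 2.3 places ERK downstream of MEK and reports MEK-dependent expression changes under a MEK inhibitor. If the baseline tumour was sampled on such a drug, its ERK targets may already be low. That pair could then show little change even if BVD-523 works, and its baseline level could mislead as a predictor of response.

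The washout does not close this gap. It limits the patient's last dose before entry, whereas the archival rule looks back as far as 6 months. A patient can satisfy the washout and still supply tissue taken on the inhibitor.

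The pre/on comparison would matter most if the trial stops at 13 patients. There would then be at most one responder, and the test of biomarker change against response could not reject.

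**Working it through.** **1. Archival route, by reading of study entry.** Take first dose as day 0 and 6 months as 182 days (assumption; 180 to 183 moves the counts by at most 2). A 3-week interval puts the latest inhibitor dose 22 days before entry.

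- Entry is first dose: latest inhibitor dose on day -22. Archival days that can be on inhibitor run from -182 to -22: 182 - 21 = 161.
- Entry is the earliest allowed consent, day -30: latest dose on day -52. Days -182 to -52: 182 - 51 = 131.
- Registration falls before dosing (4.1: "Registrations must occur prior to the initiation of protocol therapy"). At any point in the last 30 days it gives a count between these two.

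The route is therefore open under every reading. These are permitted days, not expected numbers of patients.

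**2. Fresh route.** The window opens on day -28.

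- Entry is first dose: days -28 to -22, so 7 of 28 days (the same 7 under the window in 9.0).
- Entry is registration r days before first dose: max(0, 7 - r). This gives 4 at r = 3 and 0 at r of 7 or more. Section 4.1 sets no minimum r.
- Entry is consent: 0, because of 5.2.1: "All participants must sign an informed consent document prior to the initiation of any study related procedures". A fresh biopsy then falls after the washout.

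**3. The plan's own figure.** Section 13.6 states at least 80% power for a two-sided rank-sum test at 0.1, 6 v 17, difference 1.35 SD. The exact test rejects at U of 26 or less, or 76 or more (attained size 0.0865). Simulation with normal changes gives 0.820 (60,000 runs) and 0.825 (100,000 runs). The figure is reproduced.

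**4. Weight of one pair.** One pair is 1/23 = 4.3% of an unweighted mean. If the trial stops at 13, 0.9 x 13 = 11.7, about 12 pairs, so 1/12 = 8.3%. P(0 or 1 response in 13) is 0.86 at a true rate of 5%, as 13.2 states, and 0.13 at 25%. With 1 responder v 11, the smallest exact two-sided p is 2/12 = 0.167, above 0.1.

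**5. Keeping or excluding affected pairs.** Assume k of 23 pairs, at random with respect to response, have their change reduced by 1.35 SD (range 1.0 to 2.0). Neither k nor the reduction is in the documents.

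| k | Power, pairs kept (range) | Power, pairs excluded |
|---|---|---|
| 0 | 0.82 | – |
| 2 | 0.77 (0.80 to 0.73) | 0.80 |
| 4 | 0.73 (0.77 to 0.65) | 0.74 |
| 7 | 0.69 (0.75 to 0.57) | 0.65 |

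False rejection in this neutral case stays between 0.084 and 0.088. Exclusion does not reliably gain power, so the argument for it is that the baseline becomes interpretable.

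**The case against.** **Control and records already exist.** Archival tissue is an exception that needs the principal investigator's agreement, and that investigator can refuse tissue taken on an inhibitor. Screening takes a medical history, and applying the 3-week rule means establishing the last kinase-inhibitor date. This largely stands. The medication record in 5.4 reaches back only 14 days, but source records would show the drug. What is missing is a written criterion and an analysis step that uses the dates.

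**Exposure needs several things at once.** The patient must have had a prior MAPK inhibitor, a biopsy while taking it within 6 months of first dose, and acceptance of that tissue. The documents give no rate for any of these. This stands, and the number affected may be zero.

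**Suppression is presumed.** Section 2.3 itself mentions acquired resistance to MEK inhibitors, so tissue taken at progression on such a drug need not be suppressed. This stands, so the claim is only that it may be.

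**Stronger readings that the documents do not support.**

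- A reader might infer that fresh biopsies on an inhibitor are generally permitted. Section 3.2.1 does not settle that. It holds only if entry means first dose, or registration fewer than 7 days before it.
- A reader might infer that the association test is seriously compromised. Seven affected pairs, all in non-responders, would raise false rejection to 0.20; two affected responders would cut power to 0.45. If exposure is independent of response, those allocations have probability C(17,7)/C(23,7) = 0.08 and C(6,2)/C(23,2) = 0.06. Both counts are assumed.
- A reader might treat 1/23 as a ceiling on the bias. It is only the weight of one pair; a percent change from a low baseline can reverse sign.

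**Conclusion.** The gap is real but minor. A stated substitution rule admits a baseline that cannot show whether BVD-523 itself inhibits ERK signalling, and this does not depend on how study entry is defined. The fresh-biopsy route is conditional and secondary.

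The size cannot be computed from the documents, which give no count of pretreated patients and no recovery time for ERK signalling. The conclusion rests on the drug order described in 2.3 and on the possibility, not the certainty, that a tumour sampled on a MEK or other MAPK inhibitor has reduced ERK activity. Any bias is limited to the ERK-signalling analyses behind secondary objective 3 and the related part of 13.6.

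**What to change.** 1. In 3.1.9, 5.2.1, 9.0 and 10.1, state that tissue, archival or fresh, taken while the patient is receiving a MAPK-pathway inhibitor is not used as the ERK-signalling baseline. It stays usable for GNAQ/GNA11 testing and exome sequencing. No repeat biopsy or dosing delay is required.
2. Record three items on the case report form: tissue source, biopsy date, and date of the last MAPK-inhibitor dose before that biopsy.
3. In 13.6, summarise the ERK-signalling change on pairs with an off-inhibitor baseline and report the all-pairs result beside it.

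No minimum interval off the inhibitor before the biopsy is proposed, because the documents give no recovery time on which to base one; the recorded dates let the reader judge. Archival tissue taken before a later MAPK inhibitor also stays usable, so treatment between the two samples remains a limitation in those pairs.

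The cost is wording in five sections, three form fields, and perhaps a few pairs lost from the off-inhibitor summary of a small secondary analysis. For the 6 v 17 test, neutral-case power is about 0.80 with 2 pairs excluded or 0.74 with 4, against 0.82.
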